### 3.7 Recruitment

Patients will be recruited via **three** different approaches:

- (1) Major trauma and/or critically ill patients admitted to the ED will be screened for in- and exclusion criteria at the ED. If being eligible they will be included and randomized.
- (2) Major trauma and/or critically ill internal patients who are directly admitted to the respective ICUs. Immediately after admission they will be screened and eventually included.
- (3) Major trauma and/or critically ill internal patients who are admitted through an in-house hospital transfer to the respective ICUs. Immediately after admission to the ICU they will be screened and eventually included.**

The planned study flow chart is displayed in Figure 2.

It is planned to recruit patients at the:

- Internal (CC 11 Cardiovascular Diseases) and surgical (CC 9 Traumatology and Reconstructive Surgery) EDs
- ICUs 8i and 14i (CC 7 Anaesthesiology, Operating-Room Management and Intensive Care Medicine)
- ICU 9i (CC 8 Surgery)
- ICUs 43a, 43b, 47i (CC 13 Internal Medicine with Gastroenterology and Nephrology)

All departments and wards are situated at the Campus Virchow at the Charité-Universitätsmedizin Berlin.

Practical recruitment will follow two main strategies:

(1) Participating wards and departments contact the study nurses/research assistants/researchers immediately after admission of patient potentially meeting the inclusion criteria between 7:00 and 19:00 (Monday to Sunday). In that case the study personnel will immediately approach the patient and performs the screening. If eligible, the patient is included, randomized and the intervention (in the intervention group only) is applied.

(2) Study personnel will do walk rounds and visits on all participating wards and department between 7:00 and 19:00. Because patients will be included within 6 hours after admission **to the respective ICUs**, it is possible to cover a recruitment time per day from approximately 1:00 to 19:00 (18 hours). If eligible patients are detected, screening is conducted and the patients are potentially included.

Based on the number of departments and wards and the corresponding cases per months according to the hospital statistics it is assumed, that enough patients can be recruited within the given time frames.

## **4 Methods: assignment of interventions**

### **4.1 Assignment of interventions**

A simple randomisation with a 1:1 allocation as per computer generated randomisation table will be used. The randomisation table will be created at the Department of Biometry and Clinical Epidemiology independently from the CRC.

### **4.2 Allocation concealment**

Sequentially numbered opaque sealed envelopes containing the group assignment will be prepared and used. Envelope preparation will be done by the data manager of the CRC who is not involved in any study preparation or procedures at this stage.

### **4.3 Allocation implementation**

The batch of sequentially numbered envelopes is stored at the CRC. At the morning of the daily recruitment times from 7:00 to 19:00 approximately 5 to 8 consecutive envelopes are taken and potentially used during the day. If screening reveals eligibility for the trial, the next numbered envelope will be opened by the study personnel and the patient is assigned.

### **4.4 Blinding**

Due to the nature of the intervention caregivers (e.g. nurses, doctors) and study assistants/researchers will not be blinded. The data manager will be blinded. Emergency unblinding is not foreseen.

## 5 Methods: data collection, management, analysis

### 5.1 Data collection and management

[figure not shown]
All data collectors will be trained in obtaining accurately the variables of interest (see 4.4). The six category PU classification system endorsed by the NPUAP/EPUAP (2014) will be used. The interrater agreement will be tested prior and during the trial using PUCLAS3 (Beeckman, Schonhoven 2014).

Paper source data (SD) and paper case report forms (CRFs) will be used to document all study variables of interest. All available routine patient documentation will be used as SD. This information will be obtained either from paper or electronic charts. SD collected explicitly for the study in addition to the routine documentation will be (based on 4.4):

- PU categories at heels and sacrum
- Resources associated with heel and sacral PU prevention and treatment
- Heel and sacral PU healing times
- Braden score
- Support surface
- Positioning

After SD verification via external monitoring (approximately 10%) pCRFs will be transmitted to the data manager. The data manager creates an SPSS file and data of the pCRFs are entered (single data entry). After data are entered, a random subset will be verified by an independent person (SD verification) who was not involved in the data entry so far. A summary of the data collection and management process is shown in Figure 3.

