### 3.6 Sample size

We are planning a study of independent cases and controls with 1 control per case. Prior data of the internal quality management indicate that the average PU incidence at the ICUs of the Charité is 0.06 per month. We expect that the cumulative PU incidence for experimental subjects will be 0.01 (RR 0.17). In order to test this hypothesis we will need to study 211 experimental patients and 211 control patients to be able to reject the null hypothesis that the PU incidence in the intervention and control groups is equal with a probability (power) of 0.8. The Type I error probability associated with this test of this null hypothesis is 0.05 (two-sided). We will use the chi-squared test statistic to evaluate this null hypothesis. To prevent a possible loss of follow-up of 10%, 464 patients in total are to be included. This total sample size is comparable to a previous trial using a similar intervention and design (Santamaria et al. 2013a). The “true” PU heel and sacral PU incidence in the study might be higher, because we will include only “high” and “very high risk” patients.

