## **6.4 Auditing**

The trial conduct is audited by an external monitor. The following processes will be reviewed:

- Patient enrolment/patient existence
- Consent
- Eligibility
- Allocation

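### Primary-outcome fields are entered once and then checked only in a random subset of unstated size; with about 15 events expected, they should be verified in full

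*Combined protocol and SAP*

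**What the plan says.** Data are recorded on paper forms. Section 5.1 sets out three steps.

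1. Before entry, source data are verified by external monitoring: "After SD verification via external monitoring (approximately 10" per cent). The sampling unit and the fields are not stated.
2. Entry is single: "The data manager creates an SPSS file and data of the pCRFs are entered (single data entry").
3. "After data are entered, a random subset will be verified by an independent person" who took no part in entry. The subset's size, its fields and the error rate that would prompt further checking are not stated.

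Section 6.4 adds: "The trial conduct is audited by an external monitor. The following processes will be reviewed". The list that follows names enrolment, consent, eligibility and allocation. Section 3.4 defines the primary outcome as an ulcer of category II, III, IV, unstageable or deep tissue injury at heels or sacrum, assessed at baseline and daily and counted cumulatively. Section 4.4 says the data manager is blinded. Section 6.2 plans one interim analysis at n = 232, with a stop if conditional power is below 60%.

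**The concern.** A random subset mostly checks patients without events, whereas the primary result rests on the few who have one. Because the outcome is met by a qualifying code at any site on any day, a patient's chance of a false event grows with the number of daily codes keyed. The reverse error is less likely: an ulcer recorded on several days is not erased by one wrong code. The risk is therefore mainly false events in both arms, which pull a small risk ratio towards 1. At stake are power at the final test and the futility decision, which is taken on about half as many events.

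**Working it through.** **Inputs from section 3.6.** Control: "the average PU incidence at the ICUs of the Charité is 0.06 per month". Intervention: "We expect that the cumulative PU incidence for experimental subjects will be 0.01 (RR 0.17"). Size: "we will need to study 211 experimental patients and 211 control patients", "with a probability (power) of 0.8", two-sided alpha 0.05, chi-squared test.

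**Reproducing the plan's figure.** With pooled variance and no continuity correction, n = [1.96√(2p̄(1−p̄)) + 0.842√(p₁(1−p₁) + p₂(1−p₂))]² / (p₁−p₂)². For 0.06 v 0.01 and p̄ = 0.035 this gives 210.9, so 211 per arm, with power 0.800.

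**Expected events.** 211 × 0.06 = 12.7 and 211 × 0.01 = 2.1, together 211 × 0.07 = 14.8. At 232 per arm: 13.9 + 2.3 = 16.2. The nearest whole-number split at 211 per arm is 13 v 2.

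**Final test with false events added to the dressing arm** (uncorrected chi-squared, 211 per arm):

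| True split | +0 | +1 | +2 | +3 |
|---|---|---|---|---|
| 13 v 2 | 0.0038 | 0.011 (13 v 3) | 0.026 (13 v 4) | 0.054 (13 v 5) |
| 12 v 3 | 0.018 | 0.041 (12 v 4) | 0.083 (12 v 5) | – |

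Weighting all possible results by their binomial probabilities under the design rates, the chance that the trial is significant but would lose significance is 11% with one false dressing-arm event and 26% with two.

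**Interim.** 232/2 = 116 per arm; 116 × 0.06 = 7.0 and 116 × 0.01 = 1.2, so 7 v 1. Section 6.2 gives no formula, so I assume conditional power under the current trend at information fraction t = 0.5: CP = Φ[(Z/√t − 1.96)/√(1−t)].

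- 7 v 1: Z = 2.16, CP = 0.94
- 7 v 2: Z = 1.70, CP = 0.74, continue
- 7 v 3: Z = 1.29, CP = 0.43, below 60%, stop

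Under the design rates, the interim decision lies within one changed patient outcome of flipping in 34% of trials and within two in 61%. These counts allow changes in either direction and either arm.

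**Dilution.** The documents give no error rate, so these are assumptions: e = 0.05% to 0.1% wrong codes per field; half of them landing on category II or worse; F = 15 to 60 site-day fields per patient (three sites over 15/3 = 5 to 60/3 = 20 days); no false code caught. The chance of a false event is q = 1 − (1 − 0.5e)^F. Each arm's rate becomes p + (1−p)q, and false events number about (422 − 14.8) × q.

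| e | F | q | False events | Rates | Power |
|---|---|---|---|---|---|
| 0.05% | 15 | 0.0037 | 1.5 | 0.064 v 0.014 | 0.76 |
| 0.1% | 60 | 0.0296 | 12 | 0.088 v 0.039 | 0.53 |

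**How much the planned check covers.** For a post-entry subset of share s, 15 × (1−s) of 15 event patients go unchecked after entry: 14.3, 13.5, 12.0 and 10.5 at s = 5%, 10%, 20% and 30%. Since s is not stated, these are illustrations.

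**The case against.** The other side has five arguments.

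**Coverage.** A reader might infer that most event records are never verified. The text does not establish this. It is true only if the post-entry subset is below 50%, or below 1 − 0.5/0.9 = 44% if both checks are independent random samples and both count. Figure 3, which summarises the process, is not available here and may say more. A reader might also apply the 10% figure and conclude that a check holds about 1.5 event patients, and none in 0.9^15 = 21% of draws. That percentage belongs to the step before entry, which cannot catch a keying error.

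**Fragility.** A reader might infer that one or two wrong codes generally decide the result. At 13 v 2 they do not, and the examples above put every error in the dressing arm. If errors ignore arm, two false events both fall there about one time in four (1/2 × 1/2). One in each arm turns 13 v 2 into 14 v 3, p = 0.0065. This stands and limits the claim to results near the boundary and to the interim.

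**Assumed rates.** The power loss has no source in the documents for its inputs, and 53% takes the worst value of each input that was varied. This stands. An isolated false code would also lack the treatment and healing records that a real ulcer would usually leave, so some would be noticed.

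**Audit list.** A reader might take section 6.4 to mean that the monitor never looks at the outcome. It lists audited processes and does not limit the source verification in 5.1, where ulcer category heads the data collected specifically for the study.

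**Other safeguards.** Duplicate skin examinations (3.3) and interrater testing (5.1) check the bedside assessment, not the keying. Blinding of the data manager makes errors that favour one arm unlikely. It does not prevent dilution.

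What survives is that full checking of the decisive fields is not required, and that the only check able to catch keying errors has no stated size or error threshold.

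**Conclusion.** The concern holds in limited form. No stated figure is wrong and no passages conflict. The plan uses a weaker method than it could for the fields that decide the trial, although the verifier needed is already planned. The expected event count of about 15 and the p-values follow from the plan's own rates. The interim result also rests on the current-trend form of conditional power. The fall in power to between 76% and 53% is a sensitivity range on assumed error rates and field counts, not a forecast. Any bias should mainly be towards no effect, so this is not a route to a spurious benefit. I class it as a cheap improvement.

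**What to change.** Add to section 5.1, in substance: *Before the interim analysis and again before the final analysis, the independent verifier checks the entered ulcer category at each site and the date of first ulcer against the paper form and source for every patient with any ulcer code, and the end-of-study ulcer status for every other patient. All other fields keep sample verification.* Word the end-of-study status as whether any ulcer developed during follow-up, because under section 3.3 follow-up can end with a healed ulcer. Add the primary outcome to the list in section 6.4.

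The first part catches false events, the larger risk; the second catches lost ones. The cost is some extra verification hours in a role that already exists. Sample size, alpha, trial procedures and patient care do not change.

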**Figure 3. Data collection and management**

## 5.2 Statistical methods

Depending on the level of measurement (nominal, ordinal, continuous) variables will be described using absolute and relative frequencies or arithmetic means, medians and spread parameters (minimum, maximum, interquartile ranges, standard deviations). Baseline demographic (age, gender, PU risk etc.) and clinical characteristics (e.g. medical diagnoses, duration of ventilation) of each group will be displayed in a table.

The primary end point PU incidence category II, III, IV, DTI at heels and/or sacrum will be compared using a Chi-squared test. This will be the main analysis of this primary outcome. A logistic regression will be applied to adjust for baseline covariates. An alpha level of 5% (two-sided) will be applied. Kaplan-Meier analyses and logrank test will be used to compare the times to development of a new PU between groups. Multiple Cox regression analysis will be performed to adjust for potential confounders. Data will be analysed as intention to treat.

Secondary outcomes will be analysed in a similar way. Depending on the level of measurement (nominal, ordinal, continuous) secondary outcomes will be described using absolute and relative frequencies or arithmetic means, medians and spread parameters (minimum, maximum, interquartile ranges, SDs). Chi-squared or t-tests will be applied to compare groups. In case of normality assumption being violated, the Mann-Whitney U test will be used instead of t-test.

For daily measurements, missing values will be imputed via LOCF method, and the results will be compared to those without imputation.

A cost effectiveness analysis (CEA) comparing both groups will be conducted. Quantities of used preventive dressings including labor costs for application in the intervention group and quantities of used PU treatment materials (e.g. dressings, time) will be documented. Current market prizes in Euro will be used to calculate the total costs per group. An incremental cost effectiveness ratio (ICER) will be calculated by dividing the mean differences in costs by the mean differences in effects. In order to make results comparable a similar approach like the work by Santamaria et al. 2013b will be used.

All analytic steps including the CEA will be repeated for the two subgroups heel PUs and sacral PUs.

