## 2.2 Objectives

### Primary objective

- To determine if preventive silicone dressings (Mepilex® border) applied to the heels and to the sacrum in addition to PU standard prevention reduce the cumulative PU incidence category II, III, IV, and deep tissue injury (DTI) compared to PU standard prevention alone in at high or very high risk hospital patients.

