### Secondary objectives

- To determine if preventive silicone dressings (Mepilex® border) applied to the heels and to the sacrum in addition to PU standard prevention reduce the PU incidence density category II, III, IV, and deep tissue injury (DTI) compared to PU standard prevention alone in at high or very high risk hospital patients.
- To determine if preventive silicone dressings (Mepilex® border) applied to the heels and to the sacrum in addition to PU standard prevention reduce the cumulative PU incidence category I compared to PU standard prevention alone in at high or very high risk hospital patients.
- To determine if preventive silicone dressings (Mepilex® border) applied to the heels and to the sacrum in addition to PU standard prevention reduce the PU incidence density category I compared to PU standard prevention alone in at high or very high risk hospital patients.
- To determine if preventive silicone dressings (Mepilex® border) applied to the heels and to the sacrum in addition to PU standard prevention increase days free of PUs category I, and category II, III, IV, and DTI compared to PU standard alone in at risk hospital patients.
- To determine if preventive silicone dressings (Mepilex® border) applied to the heels and to the sacrum in addition to PU standard prevention are cost effective.

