### 3.4 Outcomes

#### Primary outcome

Name	Method and metric	Time points of data collection
Pressure ulcer category II, III, IV, Unstageable, DTI at heels or sacrum	
 
• Clinical assessment using the NPUAP/EPUAP 2014 PU classification system
 
• Proportions developed from baseline until end of study (cumulative incidence)
 
	D0 and once daily

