### Category/Stage II: Partial Thickness Skin Loss

Partial thickness loss of dermis presenting as a shallow open ulcer with a red pink wound bed, without slough. May also present as an intact or open/ruptured serum-filled blister.

Presents as a shiny or dry shallow ulcer without slough or bruising.\* This Category/Stage should not be used to describe skin tears, tape burns, perineal dermatitis, maceration or excoriation.

[figure not shown]
*\*Bruising indicates suspected deep tissue injury.*

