### Category/Stage III: Full Thickness Skin Loss

Full thickness tissue loss. Subcutaneous fat may be visible but bone, tendon or muscle are not exposed. Slough may be present but does not obscure the depth of tissue loss. May include undermining and tunneling.

The depth of a Category/Stage III pressure ulcer varies by anatomical location. The bridge of the nose, ear, occiput and malleolus do not have subcutaneous tissue and Category/Stage III ulcers can be shallow. In contrast, areas of significant adiposity can develop extremely deep Category/Stage III pressure ulcers. Bone/tendon is not visible or directly palpable.

[figure not shown]

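### The primary endpoint has two category lists: Section 3.4 counts Unstageable ulcers, while the primary objective and the main-test sentence in 5.2 leave them out

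*Combined protocol and SAP*

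**What the plan says.** Three places in the combined protocol and SAP define the primary endpoint by category.

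- Section 3.4, Primary outcome table: "Pressure ulcer category II, III, IV, Unstageable, DTI at heels or sacrum", measured as cumulative incidence from baseline to end of study.
- Section 2.2, Primary objective: "reduce the cumulative PU incidence category II, III, IV, and deep tissue injury (DTI"). Unstageable is absent.
- Section 5.2, Statistical methods: "The primary end point PU incidence category II, III, IV, DTI at heels and/or sacrum will be compared using a Chi-squared test". Unstageable is absent. The next sentence identifies this as the main analysis of the primary outcome.

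The secondary incidence-density endpoint has the same mismatch. The 3.4 secondary table includes Unstageable; the objective in 2.2 reads "reduce the PU incidence density category II, III, IV, and deep tissue injury (DTI").

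Other sections do not settle the point. Section 3.6 states that "the cumulative PU incidence for experimental subjects will be 0.01 (RR 0.17") but names no categories. Section 6.2 bases the futility rule on incidences without defining the event. Section 5.1 says "The six category PU classification system endorsed by the NPUAP/EPUAP (2014) will be used", which governs recording and not which codes count as events.

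**The concern.** Unstageable is a separate code in the classification the trial uses, so a list that omits it does not include it by default. Appendix 4 describes it as full-thickness loss whose depth, and therefore stage, cannot yet be determined. No section maps it to III or IV.

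Two readings of 5.2 are open. An analyst could count Unstageable with III and IV, because Appendix 4 describes all three as full-thickness loss; its Category III entry, for example, begins "Full thickness tissue loss. Subcutaneous fat may be visible but bone, tendon or muscle are not exposed". Or the analyst could follow 5.2 as written. Then an Unstageable-only patient is a non-event, while a Category II ulcer, described as "Partial thickness loss of dermis presenting as a shallow open ulcer with a red pink wound bed, without slough", is an event.

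The event definition for the main test and for the futility rule is therefore left open in an unblinded trial that expects about 15 events. If it is settled after the data are seen, that is a post hoc decision on the primary endpoint.

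**Working it through.** **Inputs (3.6, 5.2, 6.2).** Control rate 0.06, intervention rate 0.01, 211 per arm, two-sided alpha 0.05, chi-squared test. Interim after 232 patients, taken as 116 per arm. Futility limit: conditional power 60%.

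**The plan's own figure.** With mean rate 0.035,

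n = [1.960·√(2·0.035·0.965) + 0.842·√(0.06·0.94 + 0.01·0.99)]² / 0.05² = 210.9, so 211 per arm.

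This matches 3.6, and the sample size is not in dispute.

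**Expected events.** 211·0.06 = 12.66 and 211·0.01 = 2.11, total 14.77.

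**Who is affected.** A patient recorded as II, III, IV or DTI at any daily inspection counts under both lists. Only Unstageable-only patients change status.

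**Final test.** Pearson chi-squared without continuity correction, 211 per arm:

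| Control vs intervention events | p |
|---|---|
| 13 vs 2 (on plan) | 0.0038 |
| 9 vs 2 | 0.0325 |
| 8 vs 2 | 0.0548 |
| 12 vs 4 | 0.0414 |
| 11 vs 4 | 0.0657 |

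The on-plan result survives the loss of four control events and fails at the fifth. Starting from 12 vs 4, one reclassified control patient removes significance.

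**Interim.** Section 6.2 bases conditional power on the observed data, so I use the current trend at information fraction 0.5: CP = Φ[(z/√0.5 − 1.96)/√0.5], with pooled z. Expected events are 116·0.06 = 6.96 and 116·0.01 = 1.16.

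| Events at 116 per arm | CP | Against 60% |
|---|---|---|
| 7 vs 1 (on plan) | 93.9% | continue |
| 6 vs 1 | 85.7% | continue |
| 5 vs 1 | 70.4% | continue |
| 7 vs 2 | 73.5% | continue |
| 6 vs 2 | 54.2% | stop |

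The on-plan interim is robust. With one more intervention event, a single control patient moves the decision across the limit.

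**Effect by assumed share.** Let u be the probability that an event, in either arm, is Unstageable-only. Take 0.06 and 0.01 as the rates for the full 3.4 list, so the 5.2 list has rates 0.06(1−u) and 0.01(1−u). Power sums the binomial probabilities of all outcomes with |z| > 1.96. Disagreement enumerates each full-list outcome together with its thinned version.

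| u | Events removed (14.77·u) | Exact power, 5.2 list | Lists disagree at 0.05 | Lists disagree on interim stop |
|---|---|---|---|---|
| 0 | 0 | 84.9% | – | – |
| 1% | 0.15 | 84.5% | about 0.8% | about 0.8% |
| 2% | 0.30 | 84.1% | about 1.6% | about 1.7% |
| 5% | 0.74 | 82.8% | 3.9% | 4.0% |
| 10% | 1.48 | 80.4% | 7.1% | 7.6% |
| 20% | 2.95 | 74.7% | 13.4% | 13.9% |

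At 5%, 10% and 20%, significance is lost under the shorter list in 3.0%, 5.8% and 11.8% of trials and gained in 0.9%, 1.3% and 1.6%. The pooled normal approximation behind the plan's 80% gives power of 80.0% at u = 0, then 77.9%, 75.6% and 70.3%.

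**The case against.** The best reply is that 3.4 is the section that defines outcomes, with method, metric and time points, and that 5.2 goes on to call its test the main analysis of this primary outcome. The only outcome under that heading in 3.4 includes Unstageable, so 2.2 and 5.2 can be read as shorthand. That is the most natural reading, and few analysts would knowingly exclude a full-thickness ulcer. But the protocol does not say it. Two of the three defining statements, including the one that specifies the test, use the shorter list. Nor is 3.4 uniform: its row for PU-free days omits Unstageable, so a reader cannot tell shorthand from intent.

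The second reply is that the affected group is narrow. Existing ulcers are excluded (3.2), skin is inspected daily (3.3), and DTI, which Appendix 4 says may evolve to thin eschar, counts under both lists. This stands: shares of 1% or 2% make the lists disagree in under 2% of trials. One point runs the other way. Appendix 4 says stable heel eschar is left in place, so a heel ulcer first recorded as Unstageable might never be restaged.

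Third, any trial with about 15 events has one-patient flips near the threshold, and the on-plan final and interim results are robust. That is also true. The flips show what the ambiguity could decide, not what is likely.

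Fourth, the direction of the power change depends on 0.06 referring to the full list. If it refers to the shorter list, the 3.4 definition adds events instead.

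Finally, the lack of blinding mainly affects how ulcers are recorded, and the data manager is blinded (4.4). Neither fact decides which codes count as events.

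**Conclusion.** The concern holds. The contradiction is in the text and does not depend on any assumed share: 3.4 counts Unstageable, 2.2 and 5.2 do not, and no section in the text available for review ranks the lists. Following 5.2 literally would contradict the trial's own outcome table.

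The numerical effect is probably small. It is confined to Unstageable-only patients, whose share the documents do not give. Over assumed shares of 1% to 20%, the two definitions would give different significance verdicts in about 0.8% to 13.4% of trials and different interim decisions in about 0.8% to 13.9%; the upper end is unlikely given the entry criteria and daily inspection. These figures assume that 0.06 and 0.01 refer to the 3.4 list, that the share is equal in both arms, that the test has no continuity correction, and that conditional power uses the current trend. The point deserves correction because it concerns the primary event definition in a trial with few events, and correcting it costs almost nothing.

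**What to change.** Use the 3.4 list (II, III, IV, Unstageable, DTI) in three places: the primary objective in 2.2, the incidence-density objective in 2.2, and the primary end point sentence in 5.2. Do this before the interim analysis, so that conditional power in 6.2 uses the same event definition as the final test.

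Optionally, add Unstageable to PU-free days in both 2.2 and 3.4. Those two passages already agree with each other, so this is for consistency only.

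The cost is a wording amendment. Ulcer categories at heels and sacrum are already recorded daily with the six-category system, so data collection and the stated sample size do not change.

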## 2.3 Trial design

A randomized, controlled, two arm, superiority pragmatic trial will be performed with a 1:1 allocation to the intervention and control groups. After completion of 50% of the subjects an interim analysis will be conducted to allow potential early stopping (futility stopping based on conditional power) (see 6.2).

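### With about 15 primary events expected and about 2 in the dressing arm, the supportive logistic and Cox models need a sparse-data method, above all for the heel and sacral repeats

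*Combined protocol and SAP*

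**What the plan says.** Section 5.2 makes an unadjusted chi-squared test the main analysis of the primary endpoint, with Kaplan-Meier curves and a log-rank test for time to a new ulcer. Two adjusted models are added:

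- for the binary endpoint, "A logistic regression will be applied to adjust for baseline covariates";
- for time to event, "Multiple Cox regression analysis will be performed to adjust for potential confounders".

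The section closes with "All analytic steps including the CEA will be repeated for the two subgroups heel PUs and sacral PUs", so both models are also to be fitted for each site.

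The plan does not list the covariates, limit their number or give a selection rule. It names no penalised or exact method and no fallback for few events. That ordinary maximum likelihood is meant is inferred from this silence.

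No expected event count is stated, but section 3.6 implies one. It says that "the average PU incidence at the ICUs of the Charité is 0.06 per month", uses 0.06 as the control proportion, expects 0.01 with dressings, and asks for 211 evaluable patients per arm (464 enrolled in total). It adds that the true incidence might be higher because only high and very high risk patients enter, without giving a figure.

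**The concern.** A logistic or Cox model estimates the treatment effect from the events in both arms. If the dressing arm has none, the likelihood keeps rising as the treatment coefficient falls towards minus infinity, so no finite maximum exists. Software then typically prints an odds or hazard ratio near zero with a huge standard error and a useless Wald interval. Naming the covariates would not cure this, because it happens with treatment alone in the model.

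Under the planning assumptions only about two dressing-arm events are expected, so an empty arm is a realistic outcome. It becomes more likely the better the dressing works. The adjusted analysis could then appear to contradict a clearly significant chi-squared test, or the team would have to pick another model after seeing the data. Section 4.4 says that caregivers and researchers are not blinded.

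A second issue is the number of parameters. Section 3.4 lists more than 20 other variables with a D0 value, any of which could enter a model with about 15 events.

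**Working it through.** **Inputs.** Section 3.6: control 0.06, dressing 0.01, two-sided alpha 0.05, power 0.8, 211 per arm, 464 in total (232 per arm). Section 2.3: 1:1 allocation.

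**1. The plan's own sample size.** With pooled variance, no continuity correction and a mean proportion of 0.035:

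n = [1.960 × √(2 × 0.035 × 0.965) + 0.842 × √(0.06 × 0.94 + 0.01 × 0.99)]² / 0.05² = 210.9, i.e. 211 per arm. The stated figure is reproduced.

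**2. Expected events.**
- Control: 211 × 0.06 = 12.7. Dressing: 211 × 0.01 = 2.1. Total 14.8 (5th to 95th percentile 9 to 21).
- If all 464 are analysed: 232 × 0.07 = 16.2.

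**3. Chance of no dressing-arm event, pooled endpoint.**

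| Control / dressing risk | Per arm | P(no dressing-arm event) |
|---|---|---|
| 0.06 / 0.01 (plan) | 211 | 0.99^211 = 12.0% |
| 0.06 / 0.01 (plan) | 232 | 0.99^232 = 9.7% |
| 0.10 / 0.0167, same RR (assumption) | 211 | 0.9833^211 = 2.9% |
| 0.06 / 0.02, weaker effect (assumption) | 211 | 0.98^211 = 1.4% |
| 0.06 / 0.03, weaker effect (assumption) | 211 | 0.97^211 = 0.16% |

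**4. Heel and sacral repeats, 211 per arm.** The documents give no split by site, so shares of 30%, 50% and 70% are assumed.

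| Share of events at the site | Expected events | P(no dressing-arm event) |
|---|---|---|
| 30% | 4.4 | 0.997^211 = 53% |
| 50% | 7.4 | 0.995^211 = 35% |
| 70% | 10.3 | 0.993^211 = 23% |

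If each event belongs to one site only, the chance that at least one of the two site analyses has an empty dressing arm is 2 × 0.347 − 0.120 = 57% for an even split, and 0.530 + 0.227 − 0.120 = 64% for 30/70. Patients with ulcers at both sites would lower these two figures.

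**5. What an empty arm looks like.** Take 0/211 versus 13/211.
- Chi-squared: 422 × 13 / 409 = 13.4, p about 0.0002. The main test works normally.
- Ordinary logistic regression: the odds ratio drifts to zero and the Wald p is 0.99 or higher, depending on when the iterations stop.
- Firth, unadjusted: (0.5/211.5) / (13.5/198.5) = 0.035, a finite odds ratio.

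**6. Number of parameters.** Arm plus two parameters: 14.8/3 = 4.9 events per parameter. Arm plus three: 14.8/4 = 3.7. Arm plus five: 14.8/6 = 2.5. In 400 simulated trials per setting at 211 per arm, with covariates unrelated to outcome, some coefficient was infinite in 10.5% of trials with treatment only, 13% with 6 parameters, 15% with 8 and 18% with 12. Adding one covariate of assumed 2% prevalence, such as tetraplegia might be, raised this to about 78%; there the infinite coefficient was mainly that covariate's own.

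**7. Bias when the estimate is finite.** In the same simulation, among trials with at least one dressing-arm event, the mean treatment log odds ratio moved from −1.86 (treatment only) to −1.94 (13 parameters), against a true −1.84. A second simulation (3000 trials, eight prognostic covariates with an assumed log odds ratio of 0.4 each) gave −2.04 against a true −1.94; Firth gave −1.91 and was finite in every trial. The standard error is about √(1/2.11 + 1/12.66) = 0.74, so a shift of 0.10 is about 0.13 of a standard error.

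**The case against.** The main analysis is the chi-squared test, and neither it nor the log-rank test breaks down with an empty arm. On the pooled endpoint the adjusted estimate is finite in about nine trials out of ten even under the planning assumptions, and more often if incidence is higher, as section 3.6 says it may be, or if the dressing works less well. The site figures rest on an undocumented split. All of this stands, and it limits the point to supportive analyses.

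Three stronger readings are tempting, and the documents do not support them:

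- *A reader might infer that the adjusted estimate for the primary endpoint will usually be infinite, or that the stated method simply fails.* The figure is 10–12% on the plan's own inputs. Only the site repeats reach a level that deserves the word frequent.
- *A reader might infer that the adjusted treatment effect will be badly biased or overfitted.* Average bias in finite estimates was small in both simulations. The degree of overfitting depends on how many covariates enter, which the plan does not say.
- *A reader might infer that the primary conclusion is at risk.* It is not.

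What the objection does not remove is the empty-arm problem itself. It needs a change of estimation method, not just a list of covariates.

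**Conclusion.** The point holds for the supportive adjusted models. With 14.8 expected events, about 2.1 of them in the dressing arm, ordinary logistic and Cox regression would have no finite treatment estimate in about 10–12% of trials for the pooled endpoint. For each site it is about 23–53%, and 35% with an even split.

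The pooled figure uses only the plan's assumptions. It also depends on reading 0.06 as a cumulative proportion, as the sample size calculation does, although section 3.6 states it per month. The site figures, the higher-incidence case and all covariate settings are assumptions.

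The change is worth making before the data are analysed because the breakdown is most likely when the dressing performs well and it costs almost nothing to prevent. It is a recommended improvement to the supportive analyses, not a flaw in the main test.

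**What to change.** In section 5.2:

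- Specify Firth penalised logistic regression and Firth penalised Cox regression, with profile-likelihood intervals, for the adjusted analyses, both pooled and by site.
- Name a small set of covariates measured at D0, fixed before the data are analysed. Count parameters, not variables, against about 15 events: a three-level risk category (3, 4A, 4B) uses two, so arm plus risk category already makes three parameters. Avoid rare binary covariates.
- Where a site has very few events, lead with the counts and a risk difference with an exact interval, and treat the regression as secondary.

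The exact number of covariates is a judgement for the team; what matters is that it is small and fixed in advance.

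The cost is a few sentences in the SAP and slight shrinkage of the adjusted estimate. Sample size, data collection and the main test do not change. The documents mention SPSS only for the data file and name no analysis package, so the team should confirm that its software fits Firth models of both kinds.
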